**Figure 1: 4-quadrant TAP block**

Ultrasound-guided TAP blocks are easier and safer than epidural blocks, and complications are rare. TAP blocks are generally performed with a single injection, because catheters are tricky to insert properly and are frequently dislodged, especially when they are near the surgical site. TAP blocks have been used for various types of

surgeries including open appendectomies, hysterectomies, caesarean deliveries, abdominoplasties, prostatectomies, renal transplantation, and laparoscopic procedures. In open gynecologic surgeries, cesarean deliveries, and open gastrectomies, bilateral TAP blocks provides better analgesia than placebo groups.

All anterior branches of spinal nerves communicates, each segmental nerve supplies different areas and therefore analgesic effect and sensorial distribution of local anesthetics vary. Four-quadrant TAP blocks (Bilateral Dual) were described by Borglum et al. and provides wider coverage for upper- and lower-abdominal wall incisions because there is no communication between upper and lateral TAP spaces. (Figure 1). Dual blocks combine subcostal and lateral/posterior TAP blocks, thus providing complete coverage. Four quadrant TAP blocks should be performed to have good coverage especially for any incision that goes above umbilicus.

TAP blocks only provide somatic pain relief; they therefore provide analgesia for surgical incisions, but not for visceral pain. Numerous studies show that TAP block with plain bupivacaine provided substantially better analgesia and reduced opioid consumption compared to unblocked or placebo patients for up to 24 hours. TAP blocks with conventional local anesthetics including bupivacaine, ropivacaine and levobupivacaine in TAP block provide safe and effective analgesia, but only for the initial 24 postoperative hours. Long-acting local anesthetics are an alternative that might provide analgesia through the initial and most painful postoperative days.

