### ***Primary Aims***

#### ***Primary Aim 1:***

To assess the relative effects of TAP blocks with liposomal bupivacaine, plain bupivacaine and placebo on opioid consumption in first 24 hours post surgery.

***Hypothesis.*** Opioid consumption over the initial 24 hours after major abdominal surgery is less when four-quadrant TAP blocks are performed with liposomal bupivacaine and plain bupivacaine compared to placebo. Opioid consumption will be evaluated as morphine sulfate equivalents; a difference of at least 10 mg in first 24 hours will be considered to be a clinically meaningful difference.

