#### ***Primary Aim 2:***

To assess the relative effects of TAP blocks with liposomal bupivacaine, plain bupivacaine and placebo on opioid consumption between 24 and 48 hours post surgery.

***Hypothesis.*** Opioid consumption between 24 and 48 hours after major abdominal surgery is less when four-quadrant TAP blocks are performed with liposomal bupivacaine than with plain bupivacaine or placebo. Opioid consumption will be evaluated as morphine sulfate equivalents; a difference of at least 10 mg will be considered to be a clinically meaningful difference.

Criteria for success will be 1) superiority of bupivacaine and exparel groups over placebo and noninferiority between plain bupivacaine and exparel groups in the first 24 hours of opioid consumption and superiority of exparel group over placebo and bupivacaine in the 24-48 hours opioid consumption.

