#### ***Criterion for success of each intervention in each period.***

0-24 hours: for each of bupivacaine and exparel, success will be concluded if found to be superior over placebo (i.e., less opioid consumption). As well, exparel or bupivacaine will be concluded better than the other if found superior on opioid consumption.

24-48 hours: exparel will be concluded successful if found better than both placebo and bupivacaine in the 24-48 hours opioid consumption.

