## **F. Data Analysis**

Randomized groups will be compared for baseline balance using standard descriptive statistics and the standardized difference (difference in means or proportions divided by the pooled standard deviation).

**Primary Outcomes.** *Opioid consumption.* The following tests for superiority on opioid consumption will be conducted (see type I error control below): 1) 0-24 hours post-surgery: compare each of exparel and plain bupivacaine to placebo; and 2) 24-48 hours post-surgery: compare exparel to each of plain bupivacaine and placebo. Groups will be compared using linear regression on log-transformed morphine equivalents, with results reported as ratio of geometric means between each pair of interventions.

**Type I error control across Primary outcomes 1 and 2.** We will use a parallel gatekeeping procedure to control the type I error at 5% across the 2 primary outcomes. The 2 comparisons for the 0-24 hour period will constitute Set #1, and the 2 comparisons for the 24-48 hour period will constitute Set #2. Within each set we will use the Holm-Bonferroni (HB) multiple comparison procedure among the two comparisons. If either test in the first Set is significant (HB: significance criterion of 0.025 for smaller P-value and 0.05 for the larger), analysis will continue to Set #2. Otherwise, Set #2 will not be analyzed. If analysis proceeds to Set #2, the overall alpha for Set #2 will be  $0.05 \times$  proportion of significant tests in Set #1 (i.e., Set #2 alpha = either  $0.05 \times 1$  or  $0.05 \times .5 = 0.025$ ).

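### Full Holm in Set #1 plus 0.025 passed to Set #2 after a single rejection breaks the stated 5% control (bound 7.5%); the excess appears only when one 0-24 h arm clearly works, the other equals placebo, and a 24-48 h null is true

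*Combined protocol and SAP*

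**What the plan says.** The paragraph on type I error control in Section 3.F makes an unconditional promise: "We will use a parallel gatekeeping procedure to control the type I error at 5% across the 2 primary outcomes". Set #1 holds liposomal versus placebo and plain versus placebo in 0-24 h. Set #2 holds liposomal versus plain and liposomal versus placebo in 24-48 h. Holm is used within each set.

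For Set #1 the text reads "HB: significance criterion of 0.025 for smaller P-value and 0.05 for the larger), analysis will continue to Set #2", and one significant test is enough to proceed. Set #2 then receives 0.05 times the "proportion of significant tests in Set #1 (i.e., Set #2 alpha = either" 0.05 or 0.025. With no Set #1 rejection, Set #2 is not tested.

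Two passages in Section 2 define success:

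- Under Primary Aim 2 there is a joint criterion: "Criteria for success will be 1) superiority of bupivacaine and exparel groups over placebo and noninferiority between plain bupivacaine and exparel groups" in 0-24 h, together with liposomal superiority over both comparators in 24-48 h.
- The criterion by intervention and period allows separate claims. In 0-24 h, "for each of bupivacaine and exparel, success will be concluded if found to be superior over placebo". In 24-48 h, "exparel will be concluded successful if found better than both placebo and bupivacaine in the 24-48 hours opioid consumption".

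**The concern.** Passing on alpha in proportion to the rejections in Set #1 is valid when each Set #1 test uses only its own 0.025: a rejected test frees its 0.025, and that amount moves to Set #2. Ordinary Holm does not leave it free. After the first rejection it hands the 0.025 to the other Set #1 test, which is then run at the full 0.05. If that test fails, the plan gives 0.025 to Set #2 as well. Parallel gatekeeping needs a separable procedure in the first family, such as Bonferroni or truncated Holm, and untruncated Holm is not separable.

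At stake is a stated error rate for the confirmatory tests. The branch that fails is one the plan provides for explicitly, namely one Set #1 rejection with half the alpha passed on.

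**Working it through.** **Inputs.** From Section 3.F: the rule above, applied to log-transformed consumption. From Section 3.G: ratio of geometric means 0.60, CV 0.85, 67 per group (79 at most with interim looks). Assumptions, because the documents do not give them: between-period correlation 0 to 0.8 (0.9 as an extreme), two-sided normal tests, no interim looks.

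**1. Where 5% is reproduced.** If all four nulls are true, Set #2 opens only after a Set #1 error, so the familywise error is that of Holm in Set #1: at most 5%, simulated 4.6-4.7%. If both Set #1 effects are real, only Set #2 can err, at 0.05 or less: simulated 4.1-4.6% with both arms at 0.60 and no 24-48 h effect.

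**2. Where it fails.** Let one Set #1 effect be real and detected, and the other Set #1 null be true.

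- The true Set #1 null is tested at 0.05.
- If it is not rejected, Set #2 is tested at 0.025.
- Bound: 0.05 + 0.025 = 0.075. With independent tests: 1 - 0.95 × 0.975 = 0.074.

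**3. Size at the planning values.**

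- Log-scale SD = √ln(1 + 0.85²) = 0.737; effect = -ln 0.60 = 0.511.
- At 67 per group, SE = 0.737 × √(2/67) = 0.127 and effect/SE = 4.01. Power at two-sided 0.025 = Φ(4.01 - 2.24) = 0.96 (0.98 at 79 per group).
- Rough hand check: 0.96 × 0.074 = 0.071. Simulation at zero correlation gives 6.9%. It is slightly lower because the two Set #2 tests share the liposomal arm.

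Simulated familywise error (%), one arm at 0.60 in 0-24 h, the other equal to placebo, no 24-48 h difference, at correlation 0 / 0.4 / 0.8. There were at least 1,000,000 replicates per cell, so the simulation standard error is about √(0.07 × 0.93/1,000,000) = 0.03 points.

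| Working arm, n per group | Rule as written | Set #1 at 0.025 each |
|---|---|---|
| Liposomal, 67 | 6.88 / 6.72 / 6.17 | 4.70 / 4.56 / 4.07 |
| Liposomal, 79 | 7.06 / 6.94 / 6.45 | 4.77 / 4.65 / 4.23 |
| Plain, 67 | 6.95 / 6.67 / 5.95 | 4.74 / 4.54 / 3.97 |
| Plain, 79 | 7.06 / 6.88 / 6.14 | 4.74 / 4.62 / 4.06 |

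At correlation 0.9 and 67 per group the rule as written gives 6.0% (liposomal) and 5.7% (plain). The largest cell found, with near-certain detection and one real effect in each set, is 7.4%. Counting only rejections towards less opioid, the one-arm range is 3.0-3.7% against 2.5%.

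**4. One-arm states without material excess.**

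- Liposomal at 0.60 in both periods, plain inert: 4.7-4.9%. Set #2 then contains no true null.
- Liposomal the only working arm, at 0.75 in 0-24 h: 4.7-5.2%.
- Either arm the only one working, at 0.80: 4.0-4.5%.

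**5. Error in the success claims.**

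- Claims by arm and period that rest on the two sets, one-arm case of step 3: 4.8-5.2% two-sided, and at most about 2.7% against 2.5% in the favourable direction. A false 24-48 h claim needs both Set #2 tests to reject. The rate reaches 6.4-6.9% only if plain equals placebo in 0-24 h while liposomal and plain are equal and both beat placebo in 24-48 h.
- All superiority conditions of the joint criterion met although one null is true: at most about 4.7% at ratio 0.60.

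**The case against.** The strongest reply is that the failing state contradicts the trial's premise. Section 1.C says that conventional local anesthetics in TAP blocks "provide safe and effective analgesia, but only for the initial 24 postoperative hours". The Primary Aim 1 hypothesis expects lower consumption with blocks "performed with liposomal bupivacaine and plain bupivacaine compared to placebo". Section 3.D also mixes plain bupivacaine into the liposomal arm's injection. One arm at 0.60 with the other exactly equal to placebo is remote. If liposomal is at 0.60 and plain at only 0.90, with no 24-48 h effect, the error is 2.3-2.7%. The joint criterion under Primary Aim 2 is protected because every condition must hold.

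All of that stands, and it limits the practical weight. It does not rescue the statement itself: strong control must hold for every combination of true and false nulls, and nothing else in the documents truncates Holm or restricts the 5% promise.

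A reader might infer more than the documents support, in four ways:

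- That the error is 6-7% whenever only one arm works in 0-24 h. It is not: a large, well-detected effect and a true 24-48 h null are also needed.
- That a false overall trial success is inflated. It is not (step 5).
- That the 5% promise covers every claim in Section 2. It covers only the four tests in the two sets. The 0-24 h liposomal-versus-plain superiority and noninferiority comparisons are in neither set.
- That these rates describe the trial with its interim looks. The documents do not say how the gatekeeping levels are split over the four analyses, so that rate cannot be derived.

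**Conclusion.** The concern holds as a defect in the written rule. As specified, it does not give strong control at 5%; the bound for the four tests is 7.5%. At the planning values the excess is about 1 to 2 percentage points (6.0-7.1%, or 5.7% at correlation 0.9), and only in the narrow state set out in step 3. The bound follows from the rule alone. The 6.0-7.1% rests on a fixed design, CV 0.85, ratio 0.60, 67-79 per group and an assumed correlation of 0-0.8. It should be corrected, because a confirmatory error statement is untrue as written and the remedy is short. It is not a reason to distrust the trial's joint success criterion.

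**What to change.** In the type I error paragraph of Section 3.F, test each Set #1 comparison at 0.025 with no step to 0.05, and keep the proportion rule and Holm for Set #2. The error is then bounded by 0.025 + 0.025 = 5% in the failing state, and the largest simulated value in any state was 4.95%. State also that the 5% applies to these four tests, and how their levels are divided over the interim analyses.

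Cost at 67 per group, ratio 0.60, before interim looks:

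- With both Set #1 effects real, power for a single Set #1 test falls from 97.7% to 96.1%.
- With all four effects real, the chance that all four tests reject falls from 92.5-93.4% to 89.6-90.8%, and 24-48 h success falls from about 95.3% to 95.0-95.2%.
- No sample size change is needed: an exact t calculation at 0.025 gives 54 per group for 90% power on one comparison.

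An acceptable alternative is to keep full Holm in Set #1 and open Set #2 only if both Set #1 tests are significant. This also holds the error at 5% and leaves the all-four probability unchanged, but 24-48 h success falls to 92.5-93.4%. That success also becomes nearly unattainable if one arm truly has no 0-24 h effect.

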## **Secondary Outcomes.**

*Time to return of sensation.* We will compare the 3 randomized groups on the time to detection of return of sensation (see above; i.e., when patients feels both ice and pinprick in at least 6 of the 8 designated test locations, or  $\geq 75\%$  of the covered points if the TAP block did not initially cover all eight locations) using a time-to event Kaplan-Meier analysis and log-rank test, and comparing patients on the estimated median time to return of sensation. If all patients do have return of sensation (as expected), the analysis will be equivalent to a Wilcoxon rank sum test, and so this test and the corresponding Hodges-Lehman estimator of median difference (CI) will be reported as a sensitivity analysis. The significance criterion for each of the 3 comparisons will be  $0.05/3 = 0.0167$  to control the type I error at 0.05 for the primary outcome.

*Pain score.* We will compare the 3 randomized groups on mean pain score over the first 72 hours using a linear mixed effects model in which we adjust for within-subject

correlation assuming an autoregressive correlation structure (or unstructured or other, whichever fits best; but making sure to also account for the differences in timing between the measurements) with fixed effects of treatment and categorical time. While we will assess the treatment-by-time interaction, main results will be reported collapsing over time regardless of a significant interaction.

*Opioid consumption 48-72 hours.* This will be analyzed using linear regression as with the primary outcomes.

[figure not shown]
Type I error will be controlled at 0.05 for secondary outcomes by using a significance criterion of  $0.05/3=0.017$  for each outcome.

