## **Amendments**

Amendment 1: 10/1/2021

Summary of Changes:

1. The primary outcome was changed to opioid consumption in the first 24 hours and 24-48 hours after surgery.
2. The secondary outcomes are now abdominal wall sensation with ice and pinprick, pain scores 72 hours after surgery, and opioid consumption 48-72 hours after surgery.
3. Sample Size Considerations was updated to reflect the changes in the study outcomes.

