## **Secondary Aims**

### **Secondary Aim 1:**

To assess the duration of the local analgesia (determined by pinprick and cold) in all four quadrants with liposomal bupivacaine, plain bupivacaine, and placebo after major abdominal surgery.

Hypothesis. Abdominal wall analgesia from four-quadrant TAP blocks with single-shot liposomal bupivacaine lasts longer after major abdominal surgery than the same blocks with plain bupivacaine or placebo. Our major outcome will be time from end of the block until abdominal wall sensation with both ice and pinprick recovers in at least six of eight designated locations. Two sequential evaluations will be needed to be negative and first negative time point will be accepted as the return of sensation.

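### Secondary outcomes: 0.05/3 is applied once across comparisons and once across outcomes, so the stated 0.05 control is not guaranteed

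*Combined protocol and SAP*

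**What the plan says.** All of this is in the combined protocol and SAP.

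- **Section 3.F, Secondary Outcomes, time to return of sensation.** "The significance criterion for each of the 3 comparisons will be" 0.05/3 = 0.0167. The stated purpose is "to control the type I error at 0.05 for the primary outcome".
- **Same section, pain score.** "We will compare the 3 randomized groups on mean pain score over the first 72 hours using a linear mixed effects model". No pairwise comparisons are listed and no per-comparison criterion is given.
- **Same section, opioid consumption 48-72 hours.** "This will be analyzed using linear regression as with the primary outcomes".
- **Same section, closing sentence.** "Type I error will be controlled at 0.05 for secondary outcomes by using a significance criterion of" 0.05/3 = 0.017 per outcome.
- **Status of sensation.** The Amendments page records: "The secondary outcomes are now abdominal wall sensation with ice and pinprick, pain scores 72 hours after surgery, and opioid consumption 48-72 hours after surgery". The Specific Aims, Section 2 and Section 3.E also place sensation among the secondary outcomes.
- **Hypotheses in Section 2.** Secondary Aim 1 states that analgesia with liposomal bupivacaine "lasts longer after major abdominal surgery than the same blocks with plain bupivacaine or placebo". That is two comparisons. Secondary Aims 2 and 3 name the same two.
- **Primary outcomes, for contrast (Section 3.F).** "Within each set we will use the Holm-Bonferroni (HB) multiple comparison procedure among the two comparisons", with thresholds of 0.025 and 0.05.

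**The concern.** The same fraction does two jobs. In the sensation paragraph it is split over three pairwise comparisons, so that one outcome uses the whole 0.05. In the closing sentence it is split over three outcomes, so that sensation has only a third of 0.05. The two divisions are never combined. The sensation sentence also calls sensation the primary outcome, which it no longer is, so it reads like text kept from before Amendment 1.

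The other two outcomes have a different gap. Each has a share of 0.017 but three randomized groups, and the plan does not say how many pairwise tests share that amount or how. The reference back to the primary analysis for 48-72 hour opioid use is attached to the regression model. It does not say whether Holm carries over, and the primary thresholds of 0.025 and 0.05 do not fit a share of 0.017.

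At stake are the pairwise claims on block duration, pain and late opioid use. A pairwise p-value between 0.0056 (or 0.0083) and 0.0167 can be significant or not depending on which sentence the analyst follows. That choice should not remain open until the results are known.

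**Working it through.** **1. The plan's figures.** 0.05/3 = 0.016667, which is the stated 0.0167. The stated 0.017 is the same number rounded up (used literally, 3 × 0.017 = 0.051). The rounding is not the problem.

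**2. Sensation alone.** Three comparisons at 0.0167 give a Bonferroni bound of 3 × 0.0167 = 0.05. Three equal arms share data across the pairs, so the actual error is a little lower: 4.4% by simulation. The share under the closing sentence is 1.67%, so sensation overspends by a factor of about 2.6 (4.4/1.67), and by up to 3 on the bound.

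**3. The secondary family.** Inputs from the plan are three arms, three secondary outcomes and 0.05/3. Assumptions not in the plan are two-sided tests, normal test statistics, equal arm sizes, and an exchangeable between-outcome correlation of 0 to 0.9. There were 1,000,000 replicates per setting, with all three arms equal on every outcome. The plan does not settle how pain and opioid use are tested, so four readings are shown. Bound = number of tests × 0.0167, with an outcome held to its share counting as one test.

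| Reading | Bound | Simulated, correlation 0 to 0.9 |
|---|---|---|
| (a) Sensation: three pairs at 0.0167; the other two outcomes held to 0.0167 in total each | 0.05 + 2 × 0.0167 = 8.3% | 7.5% to 5.1% |
| (b) Two pairs per outcome at 0.0167 | 6 × 0.0167 = 10% | 9.1% to 5.5% |
| (c) Three pairs for sensation, two for each other outcome, at 0.0167 | 7 × 0.0167 = 11.7% | 10.3% to 6.7% |
| (d) Three pairs for every outcome at 0.0167 | 9 × 0.0167 = 15% | 12.6% to 7.7% |

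Every reading exceeds 5% across this range of correlation. Reading (a) uses only criteria that the text states and is the most favourable to the plan.

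**4. When some arms truly differ.**

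- One arm differs from two equal arms on every outcome. One true null pair per outcome remains, each tested at 0.0167. The bound is 3 × 0.0167 = 5%. With independent outcomes the error is 1 − (1 − 0.0167)³ = 4.9%, and it falls to 3.0% at correlation 0.9.
- One arm differs on sensation only, and all arms are equal on pain and 48-72 hour opioid use. Under reading (a) the bound is 5%, with 4.9% at correlation 0. If pain and opioid use each have two pairs at 0.0167, the error is 7.7% to about 5.0%. With three pairs each it is 10.1% to about 6.8%.

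Inflation therefore comes only from outcomes on which all three arms are equal and several pairs are tested at 0.0167.

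**5. Remedies under the complete null, correlation 0 to 0.9.**

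- Overall three-group test at 0.0167 as a gate, then pairs at 0.0167: 4.9% to 3.1%.
- Holm at 0.0167 over two pairs per outcome: 4.7% to 2.9%.
- Holm at 0.0167 over three pairs per outcome: 4.5% to 2.9%.

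**The case against.** The best defence is that the two sentences can be reconciled. Sensation and pain are described as comparisons of three groups. If the 0.017 applies to the overall test and the 0.0167 to pairwise tests made only after a significant overall test, each outcome spends about 0.0167. The plan names an overall test followed by pairwise tests for satisfaction, under Tertiary Outcomes. But no such gate is written for the secondary outcomes. The sensation sentence sets a criterion for each comparison directly and says that it protects 0.05 for that one outcome. The defence has to add the rule that is missing.

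The second point has more force. Saline is not expected to block sensation, so equality of all three arms on that outcome is unlikely. If saline differs from both active arms, reading (a) stays within 5%. This stands, and the figures for the complete null are worst cases. It does not help pain or 48-72 hour opioid use. Section 1.C of the Background limits plain bupivacaine TAP blocks to about 24 hours, and Section 1.D treats liposomal benefit in TAP blocks as unresolved. Three equal arms on late opioid use are therefore quite possible.

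Third, readings (b) to (d) are not stated in the plan, and the reference to the primary analysis may be meant to import Holm. Both are fair. Those readings show the range left open by the text. They do not predict what the analysts will do.

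Finally, counting three comparisons where the hypotheses name two is conservative for sensation and is not an error in itself, since the aims speak of the relative effects of all three treatments. It does mean that the list of comparisons needs to be stated.

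**Conclusion.** The concern holds. The sensation criterion and the closing sentence contradict each other, and following both as written does not guarantee the 0.05 that the section claims. This is a wrong rule for sensation and a missing rule for the other two outcomes.

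On the reading kindest to the plan, the secondary family error is at most 8.3%, simulated at 7.5% down to 5.1%. On the least favourable reading it is at most 15%, simulated at 12.6% down to 7.7%. These figures assume that all arms are equal on every outcome, and they rest on the assumed correlations. Where one arm truly differs on every outcome, the error is 3.0% to 4.9% and there is no inflation.

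Only secondary claims are affected; the gatekeeping rule for the two primary outcomes stands apart. The correction should be made before unblinding but does not threaten the trial's main conclusion.

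**What to change.** 1. List the pairwise comparisons for each secondary outcome: either the two in the hypotheses of Section 2 (liposomal against plain, liposomal against placebo) or all three. Make the hypotheses and the analysis section agree.
2. Replace the sensation criterion with a rule under which each secondary outcome spends 0.0167 in total, and state the same rule for pain and for 48-72 hour opioid use. Either of these works:
   - **Gate.** Run the overall three-group test at 0.0167 and make pairwise comparisons at 0.0167 only if it is significant. With three groups this is a closed test.
   - **Holm at 0.0167** over the named comparisons. The smallest p-value is tested against 0.0167/2 = 0.0083 if two are named, or 0.0167/3 = 0.0056 if three.
3. Delete the reference to the primary outcome in the sensation sentence. The Economic Analysis paragraph under Tertiary Outcomes gives sensation the same outdated label and should be corrected too.
4. Write 0.0167 throughout in place of 0.017.

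The cost is a few sentences and no extra patients. Secondary pairwise claims become harder to make. Under Holm the smallest p-value must reach z = 2.64 (two comparisons) or 2.77 (three) instead of 2.39. Under the gate the pairwise criterion is unchanged, but the overall test must be significant first.
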